cortical/cancellous allograft in conjunction with an approved Depuy Synthes pedicle screw system compared to autograft mixed with cortical/cancellous allograft in conjunction with the same DePuy Synthes pedicle screw system used for a one or two- level posterolateral lumbar fusion.

Methodology

Study Design

This is a prospective randomized, non-blinded, controlled study. Patients with a diagnosis of degenerative disc disease and/or up to grade I spondylolisthesis and planning to undergo a 1- or 2-level instrumented posterolateral lumbar fusion surgery between L1-S1 will be screened. If eligible and the subject meets all the inclusion criteria and none of the exclusion criteria, the subject will be approached about study participation by the surgeon. If the subject agrees to participate, the consent process will be initiated by the study coordinator. Once the patient has been consented; data including medical history, neurological exam, patient questionnaires (VAS, ODI, SF-36) will be collected. Randomization will occur once a surgery date has been scheduled so the appropriate instrumentation can be boarded accordingly. A randomization envelope will reveal randomization treatment group. The envelopes will be generated in a 1:1 fashion and be randomly allocated to an assigned study identification number. Subjects will be randomized to either: 1) treatment arm where the investigator will use an FDA approved/cleared DePuy Synthes spinal pedicle screw system with ViviGen® Cellular Bone Matrix mixed with cortical/cancellous allograft or the 2) control arm where the investigator use the same DePuy Synthes spinal pedicle screw system with local autologous bone graft mixed with cortical/cancellous allograft. Both treatment groups represent standard of care lumbar fusion surgeries using two types of bone graft options to create the arthrodesis as comparators.

Once the lumbar fusion surgery has taken place as planned; data will be collected regarding the surgery performed, including operative time, amount of bone graft used, spinal system used, length of hospital stay, and adverse events/complications.

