Secondary endpoints (VAS, ODI, SF-36, neurological status, and fusion) will be quantified to detect changes longitudinally from baseline through 12-months post-surgery.

Study Population and Inclusion/Exclusion Criteria

Patients with a diagnosis of spinal stenosis, degenerative disc disease and/or up to grade I spondylolisthesis and planning to undergo a 1 or 2-level instrumented posterolateral lumbar fusion surgery between L1-S1 will be asked to participate in the study. If eligible, the consent process will be initiated by the study coordinator

A subject may be included if the following criteria are met:

1. ≥ 18 years of age
2. Able to provide consent
3. Is undergoing standard of care one or two-level instrumented posterolateral fusion at the level between L1-S1
4. Has diagnosis of spinal stenosis, degenerative disc disease and/or up to Grade 1 spondylolisthesis
5. Requires decompression at intended fusion level (multi-level decompression allowed L1-S1)
6. Has failed 6-weeks or more of conservative, non-operative treatment
7. Has back and/or radicular lumbar symptoms with ODI (Oswestry Disability Index) score of ≥ 30 preoperatively.

A subject will be excluded if any of the following criteria are met:

1. Any prior lumbar fusion surgery
2. Requires fusion of more than two levels
3. Requires an interbody fusion based on relevant diagnosis and factors (such as foraminal stenosis, degree of spondylolisthesis, spinal deformity, disc space collapse, and subject's age) as determined by investigator
4. BMI > 40

5. Active systemic infection or infection at operative site
6. History of an osteoporotic fracture and/or vertebral body fracture
7. Is currently being treated with chemotherapy, radiation, immunosuppression or chronic steroid therapy
8. History of osteoporosis, osteopenia, or osteomalacia that would contraindicate spinal surgery
9. Psychological or physical condition in the opinion of the investigator that would interfere with subject self-assessments
10. History of neurological condition in the opinion of the investigator that may affect lumbar function and pain assessments
11. Subjects with a history of cancer must be disease free for at least 3 years
12. Pregnant, or plans on becoming pregnant

Intervention

Treatment arm/group: 20 subjects undergoing open, one or two-level instrumented posterolateral lumbar fusion surgery using ViviGen Cellular Bone Matrix mixed with cortical/cancellous allograft and DePuy Synthes pedicle screw system.

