Control arm/group: 20 subjects undergoing open, one or two-level posterolateral lumbar fusion surgery using local autograft mixed with cortical/cancellous allograft and DePuy Synthes pedicle screw system.

Data and Safety Monitoring

The PI and study team (including sub-investigators, clinical research manager) will be responsible for data and safety monitoring. All adverse events will be reviewed to determine relatedness to the product and reported to sponsor as necessary (if related to product and unanticipated according to risk profile). The data will be reviewed for maintenance of confidentiality and integrity as well as the data collection process. The data and safety review will take place every six months from the date of the first patient enrolled into the study or after every ten patients enrolled whichever comes first.

Adverse Events

Relevant adverse events (those related to the study device, the surgical procedure, or the lumbar spine) will be recorded in this study. All adverse events will be reviewed for relatedness and expectedness by the PI on a case by case basis and per Data and Safety Monitoring guidelines.

Protocol Deviations

The investigators are responsible for documenting all protocol deviations, including an explanation for why the deviation occurred. All protocol deviations will be recorded and submitted to the IRB per policy.

Outcomes

Primary Endpoint

IRB NUMBER: 2018-158

IRB APPROVAL DATE: 10/18/2019

- Successful lumbar fusion as measured by CT scan and flexion/extension x-rays at 12-months; as evidenced by bony bridging, presence of radiolucency, no development of pseudoarthrosis

Secondary Endpoints

- Improvement in patient reported outcomes as measured by VAS (\geq 2-point improvement), ODI (\geq 15-point improvement), SF-36 (\geq 15-point improvement) from baseline to 12-months.
- No new or worsening neurological (motor and sensory) deficit as compared to baseline through 12-months. No revision surgery and/or development of pseudoarthrosis by month 12.
- No occurrence of adverse events related to device by month 12.

Subject Screening and Enrollment

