Patients who have already planned a decompressive lumbar laminectomy and fusion surgery will be approached about potential study participation. If the patient wishes to proceed with study participation, the study coordinator will go through the informed consent process. After the consent process has been completed, the subject will be further screened for eligibility and given the subject questionnaires to complete.

Screen Failures

If the subject does not meet all inclusion criteria or meets one of the exclusion criteria after signing consent, then the subject will be considered a screen failure and therefore, not enrolled into the study. The subject will also be considered a screen failure and not enrolled in the study if there is a change in surgical treatment based on the surgeon's observations and best practice intraoperatively.

Withdrawals

A subject who withdraws consent prior to study completion will be removed from the study and no longer followed. The surgery, instrumentation, and bone grafts are FDA approved and cleared and considered standard of care. The subjects may follow-up as needed and per standard of care at their own discretion if they decide to no longer participate in the study.

The reasons for voluntary withdrawal or discontinuation of study subjects will be documented. If during the course of the clinical study, a study subject is non-responsive to attempts to schedule follow-up visits, communication methods such as phone calls, emails, mail, or other means as appropriate in an attempt schedule an appointment or determine if the subject has moved, died, or otherwise become lost to follow-up.

Summary and Rationale of Proposed Study

The purpose of this study is to collect on-label safety and efficacy data where ViviGen® Cellular Bone Matrix is applied to posterolateral lumbar fusion with DePuy Synthes pedicle screw system. It is expected that this study will contribute to the compilation of clinical data required

to demonstrate the ability of ViviGen® Cellular Bone Matrix to promote safe, effective and timely spine fusion in patients who undergo posterolateral lumbar fusion surgery. The results of this study will lead to further analysis (i.e. comparison to historical data of other marketed bone graft products, as well as, to local bone alone).

References

1. Boden SD. Overview of the biology of lumbar spine fusion and principles for selecting a bone graft substitute. *Spine* 27, S26-S31 (2002).

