| Study Summary | 
All subjects who sign an IRB approved consent form are considered in active screening to determine eligibility. Once a subject is consented, the following visits will take place:
 
Baseline (\leq 60 days of surgery):
 
 • Medical history • Neurological exam (Lumbar Spine Exam, appendix 1) • Demographics • VAS, ODI, SF-36 questionnaires • Lumbar spine x-rays AP/lateral, flexion/extension or as done per standard of care • Randomization 
Surgical Visit:
 
 • Surgery performed • Operative Time • Amount of Bone Graft used • Pedicle Screw System used • Length of Hospital Stay • Adverse Events/Complications 
6-week Visit (\pm 2 weeks):
 
 • VAS, ODI, SF-36, patient satisfaction questionnaires • Neurological Exam • Lumbar AP/Lateral x-rays • Adverse Events 
3-month Visit (\pm 3 weeks):
 
 • VAS, ODI, SF-36, patient satisfaction questionnaires • Neurological Exam • Lumbar AP/Lateral and flexion/extension x-rays • Adverse Events 
6-month Visit (\pm 1 month):
 
 • VAS, ODI, SF-36, patient satisfaction questionnaires • Neurological Exam • Lumbar AP/Lateral and flexion/extension x-rays • Adverse Events 
12-month Visit (\pm 2 months):
 
 • VAS, ODI, SF-36, patient satisfaction questionnaires • Neurological Exam • Lumbar AP/Lateral and flexion/extension x-rays • CT scan of the lumbar spine without contrast • Evaluate fusion status • Adverse Events |
|---------------|---|

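### Patients whose operation changes in theatre are dropped as screen failures after randomisation with the arm known, which can bias the 12-month fusion comparison in either direction

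*Combined protocol and SAP*

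**What the plan says.** Four parts of the document bear on this.

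- **Study Design (Methodology).** "This is a prospective randomized, non-blinded, controlled study". On timing: "Randomization will occur once a surgery date has been scheduled so the appropriate instrumentation can be boarded accordingly". On disclosure: "A randomization envelope will reveal randomization treatment group".
- **Study Synopsis, Study Summary.** Randomisation is the last item under Baseline, ahead of the Surgical Visit. The same section says: "All subjects who sign an IRB approved consent form are considered in active screening to determine eligibility".
- **Screen Failures.** "The subject will also be considered a screen failure and not enrolled in the study if there is a change in surgical treatment", where the change is "based on the surgeon's observations and best practice intraoperatively".
- **Protocol Deviations.** "All protocol deviations will be recorded and submitted to the IRB per policy". The Screen Failures section does not send intraoperative changes through this process.

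The Statistical Analysis section states a non-inferiority hypothesis for fusion at 12 months with 20 patients per arm. It defines no analysis set and gives neither a margin nor an alpha. No section provides follow-up, 12-month imaging, replacement, by-arm counts or a sensitivity analysis for patients removed by this rule.

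**The concern.** A screen failure is someone found unsuitable before allocation. Here the patient already has an arm, the arm has been disclosed, and the decision that removes the patient is made during the operation by a surgeon who can know it. Randomisation protects the comparison only if those allocated are those compared.

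The arms differ in graft source, so reasons for changing the operation could differ by arm, and a patient whose operation has to be changed may also have a different chance of fusing. If the ViviGen arm loses patients who would not have fused, a non-inferiority claim becomes easier. If the control arm loses them, it becomes harder. Because removed patients are treated as never enrolled, nothing in the plan obliges the report to show how many there were in each arm, so a reader could not judge whether bias arose.

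**Working it through.** **1. Order of events.** Consent and baseline data; randomisation when surgery is scheduled; envelope discloses the arm; surgery; possible classification as a screen failure. Study Design and the Synopsis agree on this order, so the exclusion comes after randomisation.

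**2. Leverage of one patient.** With 20 per arm (Statistical Analysis), one patient is 1/20 = 5 points. Take a hypothetical arm with 17 of 20 fused, close to the plan's assumed 86%:
- no removal: 17/20 = 85.0%
- one non-fuser removed: 17/19 = 89.5%
- two non-fusers removed: 17/18 = 94.4%

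More generally, if the true rate is 0.86 and k patients with fusion probability q are removed from one arm, the remaining rate is (20 × 0.86 − kq)/(20 − k). For k = 1 this gives 90.5% (q = 0) or 85.3% (q = 1). For k = 2 it gives 95.6% (q = 0), 90.0% (q = 0.5) or 84.4% (q = 1). The shift for one or two removals thus runs from −1.6 to +9.6 points.

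**3. The plan's own sample-size figure.** The plan gives 60 patients, power 0.80, 86% fusion, a one-sided test and 10% dropout. Without a margin or alpha the 60 cannot be confirmed, but the margins compatible with it follow from margin = (z₁₋α + z₀.₈₀) × √(2 × 0.86 × 0.14 / n):

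| One-sided α (assumed) | n per arm | Implied margin |
|---|---|---|
| 0.05 | 30 (no dropout) | 0.223 |
| 0.05 | 27 (10% dropout) | 0.235 |
| 0.025 | 30 | 0.251 |
| 0.025 | 27 | 0.265 |

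**4. Effect on the non-inferiority test (illustration).** Assumptions, none of them in the plan: margin 0.235, one-sided α 0.05, unpooled Wald test, 20 per arm, no replacement. The true rates are set at the margin, 0.86 control and 0.86 − 0.235 = 0.625 ViviGen. The probability of wrongly declaring non-inferiority, by exact enumeration of both binomials, is:

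| Removed | k = 0 | k = 1 | k = 2 | k = 3 |
|---|---|---|---|---|
| ViviGen non-fusers | 0.056 | 0.110 | 0.164 | 0.283 |
| ViviGen non-fusers, replaced | – | 0.097 | 0.156 | 0.229 |
| Control non-fusers | 0.056 | 0.033 | 0.018 | 0.011 |
| k non-fusers from each arm | 0.056 | 0.078 | 0.101 | 0.118 |
| From one arm, unrelated to outcome | 0.056 | 0.056–0.061 | 0.050–0.054 | 0.044–0.064 |

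When both arms truly fuse at 86%, power under these settings is 0.709. It falls to 0.614 or 0.538 if one or two control non-fusers are removed.

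**5. Sensitivity to the assumed margin and alpha.** At margin 0.223 and α 0.05 the rate is 0.057 with no removal and 0.095, 0.187 and 0.281 after removing 1, 2 or 3 ViviGen non-fusers. At one-sided 0.025 it is 0.032, then 0.061, 0.125 and 0.191 (margin 0.251), or 0.028, then 0.062, 0.105 and 0.176 (margin 0.2645). The pattern is the same in all four settings.

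**The case against.** The best defence is that the rule works as a late eligibility check. The protocol excludes a patient who "Requires an interbody fusion based on relevant diagnosis and factors", as judged by the investigator, or who needs more than two levels fused. Such needs may become clear only in theatre, and they concern anatomy more than graft. That is partly right. But the rule covers any change of surgical treatment, without criteria, and the arm is already known.

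A second objection is to the size. The surgeon cannot foresee who will fail to fuse 12 months later. At a true rate of 62.5%, removals unrelated to outcome would all be non-fusers with probability 0.375, 0.14 or 0.05 for k = 1, 2 or 3. Removal unrelated to outcome leaves the error rate at 0.044 to 0.064, and balanced removal of non-fusers gives at most 0.118. This stands: the ViviGen-only rows are worst cases, and intermediate degrees of association were not modelled.

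Third, patients classed as not enrolled would presumably be replaced to reach 40. That is a reasonable reading, though unstated. Replacement lowers the worst-case figures only modestly and does not restore the randomised comparison.

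Fourth, analysis by assigned arm has a cost of its own: patients who had a different operation can pull the arms together, which can favour non-inferiority. This too is correct, and it is why the as-planned set should be kept alongside. Finally, envelopes are tied to study numbers, so allocations are traceable. What is missing is a commitment to report them.

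**Conclusion.** The point holds. The rule as written removes randomised patients after the arm is disclosed, and no other section offsets it. It should be corrected before analysis, and preferably while patients can still be followed, because a 12-month CT that was not done cannot be recovered.

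The firm part of the conclusion is the order of events and the leverage of single patients at 20 per arm. The error rates rest on an assumed margin, alpha and test, and on extreme selection. The documents give no expected frequency or arm balance of intraoperative changes, so the bias may be negligible or may decide the result, in either direction. The finding is that the rule allows bias and leaves it undetectable, not that bias has occurred. The surgical decision itself is not in question.

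**What to change.** - Limit screen failure to patients found ineligible before randomisation, and state that every randomised patient counts as enrolled.
- Record an intraoperative change as a protocol deviation under the existing process.
- Follow these patients to 12 months, with the same imaging, and analyse them in the assigned arm.
- State in advance how fusion is scored when the planned fusion was not carried out. One option is to apply the same CT and flexion/extension definition at the planned levels, count the patient as not fused if no fusion was performed there, and add a sensitivity analysis with these patients scored the other way.
- Exclude such patients only from a per-protocol analysis. Report both analyses, since the hypothesis is non-inferiority.
- Report the number of intraoperative changes, with reasons, by arm.

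The cost is a change of wording plus 12-month follow-up of what should be a few already consented patients. The assigned-arm analysis will be somewhat diluted by patients who had a different operation; the per-protocol analysis shows how much that matters.

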| Study Objectives | 
 • Primary Objective: 
 1. To evaluate bone fusion using ViviGen Cellular Bone Matrix for one or two-level instrumented posterolateral lumbar fusion surgery • Secondary Objectives: 
 1. To evaluate VAS, ODI, SF-36 and patient satisfaction scores postoperatively compared to baseline/preoperative. 2. Evaluate the occurrence of procedure and/or device related adverse events |

| | |
|--------------------|--|
| Study Endpoints | 
Primary Endpoint:
 
 Successful lumbar bone fusion as measured by CT scan and flexion/extension x-rays at 12-months; as evidenced by bony bridging, presence of radiolucency, no development of pseudoarthrosis 
Secondary Endpoints:
 
 Improvement in patient reported outcomes as measured by VAS (\geq 2-point improvement), ODI (\geq 15-point improvement), SF-36 (\geq 15 point improvement) from baseline to 12-months. No new or worsening neurological (motor and sensory) deficit as compared to baseline through 12-months. No revision surgery and/or development of pseudoarthrosis by month 12. No occurrence of adverse events related to device by month 12. |
| Inclusion Criteria | 
A subject may be included if the following criteria are met:
 
 1. \geq18 years of age 2. Able to provide consent 3. Is undergoing standard of care one or two-level instrumented posterolateral fusion at the level between L1-S1 4. Has diagnosis of spinal stenosis, degenerative disc disease and/or up to Grade 1 spondylolisthesis 5. Requires decompression at intended fusion level (multi-level decompression allowed L1-S1) 6. Has failed 6-weeks or more of conservative, non-operative treatment 7. Has back and/or radicular lumbar symptoms with ODI (Oswestry Disability Index) score of \geq 30 preoperatively. |
| Exclusion Criteria | 
A subject will be excluded if any of the following criteria are met:
 
 1. Any prior lumbar fusion surgery 2. Requires fusion of more than two levels 3. Requires an interbody fusion based on relevant diagnoses and factors (such as foraminal stenosis, degree of spondylolisthesis, spinal deformity, disc space collapse, and subject's age) as determined by investigator 3. BMI $>$ 40 4. Active systemic infection or infection at operative site 5. History of an osteoporotic fracture and/or vertebral body fracture 6. Is currently being treated with chemotherapy, radiation, immunosuppression or chronic steroid therapy 7. History of osteoporosis, osteopenia, or osteomalacia that would contraindicate spinal surgery 8. Psychological or physical condition in the opinion of the investigator that would interfere with subject self-assessments 9. History of neurological condition in the opinion of the investigator that may affect lumbar function and pain assessments 10. Subjects with a history of cancer must be disease free for at least 3 years 11. Pregnant, or plans on becoming pregnant |

| | |
|---------------|---|
| Study Summary | 
All subjects who sign an IRB approved consent form are considered in active screening to determine eligibility. Once a subject is consented, the following visits will take place:
 
Baseline (\leq 60 days of surgery):
 
 • Medical history • Neurological exam (Lumbar Spine Exam, appendix 1) • Demographics • VAS, ODI, SF-36 questionnaires • Lumbar spine x-rays AP/lateral, flexion/extension or as done per standard of care • Randomization 
Surgical Visit:
 
 • Surgery performed • Operative Time • Amount of Bone Graft used • Pedicle Screw System used • Length of Hospital Stay • Adverse Events/Complications 
6-week Visit (\pm 2 weeks):
 
 • VAS, ODI, SF-36, patient satisfaction questionnaires • Neurological Exam • Lumbar AP/Lateral x-rays • Adverse Events 
3-month Visit (\pm 3 weeks):
 
 • VAS, ODI, SF-36, patient satisfaction questionnaires • Neurological Exam • Lumbar AP/Lateral and flexion/extension x-rays • Adverse Events 
6-month Visit (\pm 1 month):
 
 • VAS, ODI, SF-36, patient satisfaction questionnaires • Neurological Exam • Lumbar AP/Lateral and flexion/extension x-rays • Adverse Events 
12-month Visit (\pm 2 months):
 
 • VAS, ODI, SF-36, patient satisfaction questionnaires • Neurological Exam • Lumbar AP/Lateral and flexion/extension x-rays • CT scan of the lumbar spine without contrast • Evaluate fusion status • Adverse Events |
|---------------|---|
